3.3 EXPLORATORY ENDPOINTS

Cuff closure time

The time required to close the vaginal cuff will be measured from time of conclusion of uterine excision to time of placement of the final Zip-stitch $^{\text{\tiny M}}$ clip or completion of final suture. Comparison may be made between the test and reference group.

Total surgical time

Total surgical time will be calculated based on procedure start and end times (time from first incision to final port closure). Comparison may be made between the test and reference group.

Visibility of implants in the vaginal canal

During visual inspection of the vaginal cuff at each follow-up visit, the surgeon will indicate whether implant material (either clips or suture) can be observed in the vaginal canal. Any association with adverse events, dyspareunia, or pain will also be noted.

4 STUDY DESIGN

4.1 OVERALL DESIGN

This randomized, controlled, blinded, prospective study will assess the safety and efficacy of the Zip-stitch™ Vaginal Cuff Closure System in achieving vaginal cuff closure following laparoscopic hysterectomy. This pivotal safety and efficacy study will begin at two sites and will be performed by a minimum of three surgeons but may be expanded to additional sites depending on enrollment. Additional sites may be inside or outside the United States.

The purpose of this trial is to evaluate the efficacy and safety of the Zip-stitch™ System. This will be accomplished by measure of the frequency of implant passing events and the frequency of postoperative vaginal cuff dehiscence, respectively. The observed rate of implant passing events will be numerically (not statistically) compared to a performance target of 5%.

A target of 59 women will be enrolled in a ratio of 2:1 test to reference (39 test and 20 reference subjects). This is based on a goal of 35 test subjects and an expected 10% of patients lost to follow-up. (See Section 9 for additional details).

During a pre-operative visit, a co-investigator surgeon may broach participation in this trial with candidate subjects. Potentially interested subjects will then be approached by a study coordinator or co-investigator surgeon other than their primary care provider to discuss study details and informed consent. Once obtained, surgery will be scheduled for interested participants.

Study enrollment will occur during surgery following satisfaction of all intra-operative exclusion criteria. This will take place after successful colpotomy, prior to initiation of vaginal cuff closure. Once enrolled, subjects will be randomized to receive cuff closure with either Zip-stitch™ or with VICRYL™ suture. Sealed randomization envelopes stratified by site and in variable block sizes will be provided in a blinded 2:1 ratio of test to reference cases. After randomization, the investigator surgeon will attempt to approximate and close the vaginal cuff using the assigned device. Integrity of the achieved closure will be visually assessed during each procedure, and laparoscopic video of cuff closure will be saved. Subjects will be blinded to the treatment they receive.

Follow-up will take place in person at one week, six-weeks, and six-months, as well as by telephone at 12-months. Follow-up will be performed by an independent co-investigator who is blinded to the treatment received (investigator who did not complete the procedure and does not have access to the blinded treatment assigned). Data capture will be performed using a validated electronic data capture system (MedNet Solutions, Minnetonka, MN).

Evaluation of the primary study endpoints will be complete after the six-week in-person follow-up visit. Secondary endpoint results will also be collected through the six-month visit and additional data will be collected through 12-months. The primary analysis of the data from this study will be performed when the six-week data are available. Data collected after 6 weeks will be reported in supplemental follow-up reports.

4.2 SCIENTIFIC RATIONALE FOR STUDY DESIGN

The primary objective of this study is to evaluate the efficacy and safety of the Zip-stitch™ Vaginal Cuff Closure system. This will be accomplished by measure of the frequency of implant passing events and the frequency of postoperative vaginal cuff dehiscence, respectively.

This study has been sized and designed in response to FDA recommendations regarding primary safety and efficacy concerns. Determination of rate of implant passing and determination of failed vaginal cuff closure are evaluable within the sample size previously proposed by the Agency.

As the primary efficacy endpoints are not comparative to the reference arm, the 2:1 reference group sizing is appropriate for the reference arm of this study. There are limitations to this reference group sizing strategy; primarily, smaller sample sizes provide weaker comparative information for safety and secondary endpoints.

Evaluation of the primary study efficacy endpoint is subject to reporting bias. It is possible that a patient may not realize she has passed an implant, or she may incorrectly report that she has passed an implant. She could, alternatively, pass or report passing multiple degraded part(s) of a single implant. To encourage accurate primary endpoint data collection, patients will be asked to collect and provide to their surgeon(s) any solid objects passed during the post-operative period. If patients do not have a visit schedules within two weeks of reporting an implant passing event, they will come in for an unscheduled

visit as soon as is practical. Events will be recorded as implant passing events only if study personnel can confirm that an implant (or part of an implant) was passed.

Due to the nature of implant passing, the data imputation strategy for the analysis of the primary study efficacy endpoint will exclude from analysis any incomplete follow-up from subjects lost to follow-up prior to their six-week follow-up visit. For example, one-week follow-up data from a subject lost to follow-up between one and six weeks will be included, but the uncompleted six-week data will be excluded, and they will not be included in the efficacy endpoint population totals for uncompleted follow-up timepoints. However, as detailed in the data imputation section of this protocol (Section 9.4.10), sensitivity analysis will be performed on primary endpoint evaluation where all missing data are imputed as successes and separately as failures. Every effort will be made to minimize missing data.

As implant passing is expected to be a spontaneous event with a low occurrence rate (<10%), any method of assumed incidence prior to six weeks is not practical. Instead, exclusion of lost subjects from both the numerator and denominator of implant passing analysis prevents biased subject exclusion and misrepresentative increases in endpoint population size. Furthermore, subjects who experience an implant passing event are more likely to report such an experience than subjects who experience no such event and therefore exclusion of lost subjects from the population total provides the strictest imputation strategy for this endpoint. After completion of six-week follow-up, implant passing data may be imputed for unblinded supplementary reporting based on average existing implant passing data. However, as the primary study endpoints conclude after six weeks, this imputation will be for supplemental analysis only. After six months clips have sufficiently degraded and are therefore unlikely to pass, and even less likely to be identified as having passed by a patient.

It is not expected that the primary study safety endpoint will be subject to reporting bias. As a significant clinical event, vaginal cuff dehiscence is unlikely to not be reported or to be subject to recall bias.

Study recruitment is designed to avoid any potential coercion. Potential subjects will have decided with their doctor to undergo minimally invasive hysterectomy prior to discussing possible participation in this trial. Once a potential candidate has been successfully pre-screened, the informed consent process will be conducted by a study investigator or coordinator other than the potential subject's doctor.

Study enrollment takes place during surgery. Intra-operative enrollment criteria are designed to specifically evaluate closure of the vaginal cuff during laparoscopic hysterectomy, the step Zip-stitch™ is designed for. Subjects who may have unforeseen complications during the anesthesia or colpotomy process for example, are not intended for treatment and their procedure should continue according to standard of care.

Study randomization will take place via blinded, variable block size randomization envelopes stratified by site. Subjects will be blinded to the treatment they receive, but as the operating surgeon cannot be blinded to the treatment provided, this study cannot be fully double-blinded. Every effort will be made to minimize opportunities for unblinding during post-operative data collection. In particular data collection will be performed by a different investigator surgeon without access to the blinded to treatment assignment, including through the electronic data capture system.

Data unblinding will take place after completion of six-week follow-up. This enables reporting of the primary study endpoints and most secondary study endpoints. The data collected at the 6 and 12-month follow-up visit and telephone call are limited to dehiscence, pain, dyspareunia, and adverse events. Adverse events are likely to have significant clinical sequelae, and therefore not likely to be forgotten. Pain and dyspareunia are evaluated based on experience in the time frame of the call, and therefore are not affected by recall bias. No statistical comparisons are being made using 12-month data.

Protocol QD-PRO-045 Rev 005

Some secondary endpoints evaluate incidence and rate of various events; others compare test and reference groups. Comparisons will be made using two-sided Fisher's Exact Tests. Secondary endpoints are not powered to reach statistical significance but are intended to provide additional information and indicate possible safety and efficacy trends.

The schedule of follow-up has been designed to assess vaginal cuff wound recovery one week after the procedure and six weeks after the procedure, when the vaginal cuff is expected to be significantly if not completely healed. The six-month in person follow-up visit will assess longer term recovery, and the 12-month follow-up phone call is timed to collect additional long-term data about subject recovery and return to normal life. Telephonic follow-up at 12-months is appropriate for this study as a physical exam later than six months is unnecessary and burdensome for subjects. Requiring long-term in-person follow-up risks loss to follow-up, and all data to be collected after six months can be collected over the phone. The FSFI has been validated for telephonic administration, ^{29,30} as has an 11-point numerical pain scale. Implant passing is not expected beyond six months as clips degrade between 5 and 8 months, and adverse events have clinical sequelae significant enough to avoid recall bias.

Use of the sexual pain and discomfort domain of the validated FSFI is a valuable but limited evaluation of post-operative dyspareunia. The FSFI has been validated only in its entirety, and therefore use of a subset of questions does not allow for conclusions that may otherwise be possible full through use of the full FSFI. However, only the sexual pain and discomfort domain of the FSFI is relevant to the outcomes of this trial, and due to length and content the full FSFI is unnecessary and burdensome.

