3.1 PRIMARY ENDPOINT

(Efficacy) Frequency of Implant Passing Events

Frequency of implant passing events will be reported for all subjects. Failure in this endpoint is defined, on a per patient basis, as the presence of one or more spontaneous implant passing events. A single event may be one or more clips or sutures being spontaneously passed by the patient (*i.e.*, not removed by medical staff).

Frequency of implant passing (either clips or sutures) will be explicitly collected at each follow-up visit; however, events may be reported between visits or during unexpected visits. When implant passing is reported, subjects will be asked to collect and provide passed implants, and an in-person evaluation will be performed. This will involve a visual cuff closure and healing assessment.

In the final analysis of this primary efficacy analysis, the rate of implant passage will be reported through six weeks. The primary objective of this endpoint is to observe a study population failure rate of less than 5% and is neither statistically-driven nor comparative.

(Safety) Frequency of Vaginal Cuff Dehiscence

Vaginal cuff dehiscence is defined as rupture of the surgical wound requiring surgical re-intervention. The proportion of subjects who experience vaginal cuff dehiscence up to six weeks after surgery will be evaluated. In the final analysis of this primary safety endpoint, failure will be reported, and test and control groups will be compared using Fisher's exact test to assess for a possible difference between groups.

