9.4.10 MISSING DATA & DATA IMPUTATION

Because implant passing is expected to be spontaneous, missing data will not be imputed for analysis of the primary study endpoint. Instead, if a subject is lost to follow-up prior to their six-week in-person visit, they will be included in the ITT population, but any incomplete data collection will be excluded from the total population evaluated for the primary study endpoint. For example, completed one-week follow-up data from a subject lost to follow-up between their one and six week visits will be included, but the uncompleted six-week data will be excluded, and they will not be included in the efficacy endpoint population totals for uncompleted follow-up timepoints. Data may be imputed based on existing data averages for subjects lost to follow-up after their six-week visit as part of additional study analysis, such as the 12-month unblinded follow-up reporting.

Sensitivity analysis will be performed on ITT population evaluation of the primary endpoint where all missing data are imputed as successes and separately as failures. Results of these analyses will be presented alongside primary endpoint evaluation. Every effort will be made to minimize missing data.

Additionally, any cases of vaginal cuff closure performed with a rescue method in accordance with protocol Section 6.5.1 will have their primary endpoint value set to missing. Their values will be imputed using multiple imputation. Additional information will be provided in the statistical analysis plan (SAP). These cases will also be included in sensitivity analysis determining possible effect of exclusion of these subjects from primary endpoint analysis.

Data imputation may be performed for appropriate secondary endpoints. Imputation will only be performed for secondary endpoints evaluating, or based on evaluation of, a status (as opposed to an incidence) and if a subject is lost to follow-up *after* their six-week visit. Data for subjects lost to follow-up before their six-week visit will not be imputed. Secondary endpoints that may allow for data imputation include (1) status of cuff closure, (2) status of cuff healing, (6) change in dyspareunia, and (7) change in pain.

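### The protocol is inconsistent on whether a confirmed implant-passing failure still counts when the woman is later lost before six weeks

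*Combined protocol and SAP*

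**What the plan says.** Section 3.1 sets the endpoint: "Failure in this endpoint is defined, on a per patient basis, as the presence of one or more spontaneous implant passing events". The rate is reported through six weeks, and the aim is to "observe a study population failure rate of less than 5" percent. A completed six-week visit is not part of the failure definition. Section 4.2 adds a confirmation step: "Events will be recorded as implant passing events only if study personnel can confirm that an implant" or part of one was passed. Section 9.4.2 asks a woman who reports an event to attend within two weeks, at an unscheduled visit if necessary.

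For women lost before the six-week visit, Section 9.4.10 says "they will be included in the ITT population, but any incomplete data collection will be excluded from the total population evaluated" for the primary endpoint. It adds that "completed one-week follow-up data from a subject lost to follow-up between their one and six week visits will be included", and that "they will not be included in the efficacy endpoint population totals for uncompleted follow-up timepoints". Section 4.2 gives the same rule and then its rationale, in two statements: "exclusion of lost subjects from both the numerator and denominator of implant passing analysis prevents biased subject exclusion", and "exclusion of lost subjects from the population total provides the strictest imputation strategy for this endpoint".

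Sections 4.2 and 9.4.10 plan sensitivity analyses with all missing data set to success and, separately, to failure. Section 9.4.10 has them presented next to the primary result. Sections 9.1 and 9.2 make the comparison with 5% numerical, with a 95% confidence interval and no formal test.

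**The concern.** Take a woman who passes a clip, has it confirmed, and is lost before six weeks. Under 3.1 her outcome is already complete. Under the data-level rule in 9.4.10 her completed data stay, but she is left out of the total for the uncompleted six-week timepoint. Under the rationale in 4.2 she leaves the numerator as well. Removing a woman from a numerator has an effect only if she had an event, so taken literally that phrase concerns exactly these women. No section says how she enters the single through-six-weeks rate, and two analysts could follow the plan and report different results.

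The claim of strictness does not cover her. Dropping an event-free lost woman gives a higher rate than counting her as a success (1/35 against 1/39). Dropping a woman with a confirmed event gives a lower one. At stake is the statement that the 5% target was or was not met, which a single event can decide.

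A related conflict concerns investigator discontinuation. Section 7.1 allows discontinued women to be left out of the analysis. Section 7.2 keeps women withdrawn by an investigator in the ITT population for the primary endpoint, and 9.3 puts every randomized woman in ITT. This is a separate matter and is not in the figures below.

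**Working it through.** **Inputs.** Test-arm goal 35 evaluable, 10% loss, 39 enrolled, maximum 44 (4.1, 9.2). Target: observed rate below 5% (3.1).

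**The plan's own figure.** 35/(1 − 0.10) = 38.9, rounded up to 39. This reproduces.

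**How many events decide.** 1/20 = 5.00% misses and 1/21 = 4.76% meets; 2/40 = 5.00% misses and 2/41 = 4.88% meets. So from 21 to 40 evaluable women one event meets the target and two miss it. From 41 evaluable, which needs enrolment above the goal of 39, two meet it and the third decides.

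**Illustration (assumed counts).** 39 enrolled, 4 lost, one event among 35 completers, one confirmed event in a woman later lost. The plan names no interval method; Clopper-Pearson is assumed.

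| Handling | Rate | 95% CI | Below 5%? |
|---|---|---|---|
| Her event removed | 1/35 = 2.9% | 0.1% to 14.9% | yes |
| Her event counted, other lost women excluded | 2/36 = 5.6% | 0.7% to 18.7% | no |
| Her event counted, other lost women as successes | 2/39 = 5.1% | 0.6% to 17.3% | no |
| She is classed as missing; missing = success | 1/39 = 2.6% | 0.1% to 13.5% | yes |
| She is classed as missing; missing = failure | 5/39 = 12.8% | 4.3% to 27.4% | no |

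With one event in each group, the first two rows disagree at every completer count from 30 to 39. At 40 completers both meet (2/41).

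**Direction.** Let a be completers with an event, b completers without, and e lost women with a confirmed event. Then (a+e)/(a+b+e) is never below a/(a+b), so removal can only help the device.

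**Average effect.** The documents do not give the passing rate, the share of loss before six weeks, or the timing. Assumed: true passing p = 5%, event time uniform over days 0 to 42, loss time uniform over days 7 to 42, loss unrelated to events, loss before six weeks q = 2.5%, 5% or 10%, and confirmation lag 0, 7 or 14 days. The chance c that an event is confirmed before loss is:
- lag 0: 24.5/42 = .583
- lag 7: 17.5/42 = .417
- lag 14: (28²/2)/35/42 = 11.2/42 = .267

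Each woman is a completer with an event, probability (1−q)p; a completer without, (1−q)(1−p); lost with a confirmed event, qpc; or otherwise lost. Exact enumeration at n = 39 gives the chance of meeting the target:

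| q | Removed | Counted, lag 0 / 7 / 14 | Gap in points |
|---|---|---|---|
| 2.5% | .4270 | .4188 / .4211 / .4232 | 0.8 / 0.6 / 0.4 |
| 5% | .4414 | .4246 / .4294 / .4337 | 1.7 / 1.2 / 0.8 |
| 10% | .4711 | .4365 / .4462 / .4551 | 3.5 / 2.5 / 1.6 |

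The chance of at least one such woman is 1 − (1 − qpc)^39: at lag 0, 2.8%, 5.5% and 10.8% for the three loss rates; at lag 14, 1.3%, 2.6% and 5.1%. About 30% of affected trials reverse, none against the device. At 44 enrolled and 10% loss the gap is .5012 − .4721 = .0291 at lag 0 and .5012 − .4877 = .0135 at lag 14.

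**Bias of counting the event.** If loss is unrelated to events, the completers-only rate averages 5.00%. Counting the event gives approximately [(1−q)p + qpc]/[(1−q) + qpc]. At q = 10%:
- lag 0: (.0450 + .0029)/(.9000 + .0029) = 5.31%
- lag 14: (.0450 + .0013)/(.9000 + .0013) = 5.14%

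**The case against.** A reader might infer that the plan orders confirmed failures to be deleted. The documents do not support that. The operative rule in both 4.2 and 9.4.10 excludes incomplete follow-up and keeps completed data. Section 9.4.10 never mentions the numerator. The argument in 4.2 that women with events are more likely to report them makes sense only if reported events stay in. Keeping the event is the better reading, and the numerator phrase sits in a rationale sentence. This stands: it is an ambiguity, not a deletion rule.

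A reader might also infer that a reversal would go unseen. If the woman is classed as missing, it would not. The missing-as-failure analysis adds her and every other lost woman as failures, so it misses 5% whenever counting her misses 5%, and it is shown next to the primary result. That stands, with limits. The plan does not class her as missing, the missing-as-success analysis would still hide her event, and missing-as-failure is not specific to this problem (5/39 in the illustration).

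Third, letting lost women into the denominator only when they failed biases the rate upward if loss is unrelated to events. That may be what 4.2 means by biased exclusion. This also stands, and the fix should be presented as a trade-off.

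Finally, the upper figures are ceilings: they need all 10% loss before six weeks and immediate confirmation. The illustration is chosen to straddle the threshold.

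**Conclusion.** The inconsistency is real and touches the primary efficacy statement. Section 3.1 counts a woman with a confirmed event as a failure. The rationale in 4.2 can be read to remove her, and its claim of strictness is wrong for her. Within 21 to 40 evaluable test women, one such event can turn a missed target into a met one, and never the reverse.

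The expected effect is small: about 0.4 to 3.5 points in the chance of meeting the target across 2.5% to 10% loss, and 0.4 to 1.6 points with a 14-day lag. These figures rest on 39 women, 5% true passing, the assumed timing, and loss unrelated to events. Because the comparison with 5% is numerical, no test or error rate is affected. The wording should still be settled before unblinding, so that the reading is not chosen with the result in view.

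**What to change.** - In 4.2 and 9.4.10, state that a woman with a passing event confirmed through six weeks, at a scheduled or unscheduled visit, counts as a failure in numerator and denominator regardless of later loss, withdrawal or discontinuation.
- State that, among lost or discontinued women, only those who are event-free with incomplete follow-up are missing, and apply this in both sensitivity analyses.
- Delete the phrase about numerator and denominator and the claim of strictness from 4.2.
- State the downside: the resulting rate is slightly conservative if loss is unrelated to events. Report the completers-only rate beside it, or a Kaplan-Meier six-week estimate as a supportive analysis.
- Separately, reconcile the analysis-exclusion clause in 7.1 with 7.2 and 9.3.

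The rescue-closure rule in 9.4.10 is not changed by this. The cost is a few sentences and one supportive rate. No new data, visits or subjects are needed, and the reported rate may be slightly less favourable.
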